10. ANALYTIC PLAN

We will describe MESA participants screened, enrolled, and completing this ancillary study according to CONSORT guidelines and compare characteristics of participants who do and do not pass through each of these stages. Primary analyses will include participants who complete baseline and 16-week follow-up regardless of adherence. Secondary analyses will include all consented participants using multiple imputation to address data missing from the 16-week follow-up visit.

We will construct linear models for the follow-up value of each outcome variable to determine whether common and rare polymorphisms in six candidate genes modify vitamin D₃ treatment effects: *CYP2R1*, *CYP24A1*, *CYP27B1*, *CYP3A4*, *SULT2A1*, and *VDR*. Independent variables in the model will include treatment group, number of minor alleles at a given locus, the interaction between treatment group and number of minor alleles, the baseline value of the outcome variable, and the following preselected precision variables: age, gender, BMI, season, and the estimated glomerular filtration rate (GFR). Given sample size limitations we will conduct primary genetic analyses among only the white and Black subgroups with potential associations carried to the Chinese and Hispanic groups. Power to detect genetic associations of common variants are shown in Table 1. Secondary genetic analyses are planned to explore all measured and imputed genetic variants with >5% minor allele frequency derived from the Affymetrix 6.0 chip and 1000 Genomes imputation using the regression framework described above.

Table 1. Power for analyses of common variants.

Minor allele frequency	All	White	Black
0.1	0.013	0.001	0.001
0.2	0.141	0.013	0.006
0.3	0.357	0.045	0.021
0.4	0.521	0.083	0.041

We will test whether race/ethnicity, gender, body mass, index, estimated GFR, and serum concentrations of 25(OH)D, bioavailable 25(OH)D, and 24,25(OH)₂D₃ modify the response to vitamin D₃ treatment using analogous regression models to those described above.

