At the time of Exam 6, MESA study personnel will approach potentially eligible subjects, confirm eligibility criteria, explain ancillary study details, and answer relevant questions. MESA personnel will then obtain informed consent for those participants who are found to be suitable and interested in this study. All hands-on recruitment procedures will be performed at the MESA field centers described above within MESA Exam 6.

B. Sources of material

As part of MESA Exam 6, participants will complete a series of interviews and questionnaires regarding their medical and surgical histories, medication use, family history, symptomatology, dietary habits, and socioeconomic status. Exam 6 participants will undergo a brief physical examination, which includes measurements of height, weight, and blood pressure, and will provide fasting blood and urine specimens. DNA was collected at the baseline MESA examination in 2000-2002 among participants who consented to genetic testing. Gentotyping was performed from participant DNA in 2009 on the Affymetrix Genome-Wide Human SNP Assay 6.0 (Affymetrix, Inc., Santa Clara, CA) and in 2012 on the HumanExome BeadChip v1.0 (Illumina, Inc., San Diego, CA).

For this trial we will ask participants to complete a brief questionnaire regarding the amount of time spent outdoors and the amount of body surface that was exposed to sunlight during the previous month. A total of 1.0 ml of collected serum and 1.0 ml of collected urine from Exam 6 will be shipped to the University of Washington Department of Laboratory Medicine for measurement of biomarkers relevant to this ancillary study: serum 25-hydroxyvitamin D, 1,25-dihydroxyvitamin D, 24,25-dihydroxyvitmain D, vitamin D binding globulin, parathyroid hormone, albumin, and creatinine, and urine calcium and creatinine. Study medication will be dispensed to all enrolled participants at Exam 6 (section C, below).

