The overall design of the study has not changed. INVITE remains a randomized two-arm, double-blind clinical trial with a 3:1 ratio of assignment to active vitamin D treatment versus placebo. We discussed the possibility of removing the placebo group to create a treatment only study; however, implementing such a change after recruitment of greater than 75% of participants would be difficult to explain to the DSMB, the MESA study sites, and the participants themselves. Moreover, we believe that such a change in design would diminish the impact of manuscripts resulting from this study.

Unlike typical event driven trials, INVITE seeks to identify characteristics that modify the response to treatment. To increase study power to detect such associations, we will start by evaluating only participants who are treated with active vitamin D to assess main effects of genetic polymorphisms and clinical characteristics on the changes in study outcomes. In parallel we will present analytic results from our original approach, in which we analyze all participants and test the interaction of relevant exposures with treatment assignment.

Changes to sample size and study power

Study power for the treatment only analytic approach is considerably greater than that of the original interaction-based analyses. Differences in the effect of vitamin D treatment on study outcomes of change in parathyroid hormone, 1,25-dihydroxyvitamin D, and urine calcium to creatinine ratios according to a modifying genetic polymorphism are presented below. Under the anticipated sample size of 682, the INVITE study will maintain power to detect clinically relevant associations. The INVITE DSMB, which includes a faculty biostatistician, met on September 13, 2018, at which time it reviewed and approved these changes to the analytic plan and power.

Figure2. Minimal detectable associations for genetic polymorphisms under a treatment-only analysis.

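### Rare variants get the single-locus model meant for common ones; at an assumed MAF of 1%, 81%/88% of White/Black tests in the parallel interaction analysis would have two or fewer placebo carriers

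*Combined protocol and SAP*

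**What the plan says.** Protocol section 10 describes linear models for the follow-up value of each outcome, built "to determine whether common and rare polymorphisms in six candidate genes modify" the treatment effect. The genetic terms are "number of minor alleles at a given locus, the interaction between treatment group and number of minor alleles", alongside treatment, the baseline value and precision covariates. Because of sample size, "we will conduct primary genetic analyses among only the white and Black subgroups". On power, "Power to detect genetic associations of common variants are shown in Table 1"; that table runs from MAF 0.1 to 0.4. The only MAF threshold in the text is above 5%, and it belongs to the secondary genome-wide analyses.

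The Analytic Plan cuts the sample from 1,600 to 682 and keeps 3:1 allocation. Under Changes to the analytic plan it reorders the work: "we will start by evaluating only participants who are treated with active vitamin D to assess main effects of genetic polymorphisms", with the interaction analysis of all participants presented in parallel. Figure 2 is captioned "Minimal detectable associations for genetic polymorphisms under a treatment-only analysis"; its content is not shown.

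Protocol section 12.1.B says that "DNA was collected at the baseline MESA examination in 2000-2002 among participants who consented to genetic testing", and that genotyping was done on a genome-wide array and "in 2012 on the HumanExome BeadChip v1.0". The genotypes needed to count carriers are therefore already held, at least for those who consented.

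The readable text nowhere defines rare, sets a minimum number of carriers, or names a gene-level test.

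**The concern.** A treatment-by-genotype interaction needs carriers in both arms. Placebo is a quarter of the sample, the subgroups divide it further, and the total has more than halved. For a rare variant the placebo side may hold one or two carriers, or none. With none, the interaction coefficient cannot be estimated. With one or two, it is estimated so poorly that only very large effects could be seen.

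Rare variants are a named part of the genetic aim, and the Introduction presents them as a strength over other trials. The risk is a set of results that are missing or uninformative, with nulls then read as evidence that rare variants do not modify the response.

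**Working it through.** **The plan's own figure.** Table 1 is the only readable power figure. It gives no significance level, effect size or SD, so it cannot be reproduced, and no error in it is claimed. It has no row below MAF 0.1.

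**Inputs.** N = 682 and 3:1 allocation (Analytic Plan). Shares of 44% White and 36% Black (protocol 12.1.A) describe Exam 5 attendees due at Exam 6, so applying them to enrollees is an assumption. The MAFs and Hardy-Weinberg proportions are also assumed.

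**Arm sizes.** White: 682 × 0.44 = 300, so 75 placebo and 225 active. Black: 682 × 0.36 = 245.5, so 61 and 184. White and Black combined: 136 and 409. All: 170.5 and 511.5.

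**Placebo carriers.** A person carries the variant with probability q = 1 − (1 − MAF)², which is 0.0199 at MAF 1%. The number of carriers is Binomial(n, q).
- White, MAF 1%: P(0) = 0.99^150 = 0.222; P(1) = 0.337; P(2) = 0.253; sum 0.812.
- Black, MAF 1%: P(0) = 0.99^122 = 0.293; P(two or fewer) = 0.878.

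**Detectable interaction** (80% power, nominal two-sided 5%, common-SD units): 2.80 × √(1/c_placebo + 1/c_active), with c = 2 × n × MAF. White, MAF 1%: 2.80 × √(1/1.50 + 1/4.50) = 2.64 SD. Black: 2.80 × √(1/1.22 + 1/3.68) = 2.92 SD.

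| MAF (assumed) | Two or fewer placebo carriers, White/Black | None | Detectable interaction, SD |
|---|---|---|---|
| 0.5% | 96% / 98% | 47% / 54% | 3.7 / 4.1 |
| 1% | 81% / 88% | 22% / 29% | 2.6 / 2.9 |
| 2% | 43% / 56% | 5% / 9% | 1.9 / 2.1 |
| 3% | 17% / 29% | 1% / 2% | 1.5 / 1.7 |
| 5% | 1.9% / 5.5% | below 0.2% | 1.2 / 1.3 |

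**Pooled, MAF 1%.** White and Black combined: 49% with two or fewer, 6.5% with none, detectable about 2.0 SD. All participants: 34%, 3.3% and about 1.75 SD.

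**Sensitivity, MAF 1%, two or fewer placebo carriers.** Shares moved by 10 points either way: 72–89% White, 80–94% Black. Cohort-design shares of 40%/30% (protocol section 4): 85%/92%. Assumed 10% loss: 85%/90%. At 1,600 participants: 32%/45%.

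**Active-only analysis, MAF 1%.** Expected carriers are 225 × 0.0199 = 4.5 White and 184 × 0.0199 = 3.7 Black. Detectable effect: 2.80/√4.50 = 1.3 SD and 2.80/√3.68 = 1.5 SD; all active participants, 2.80/√10.2 = 0.9 SD.

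**Size of the interaction test** (simulated; 75/225 participants with 4/11 or 7/22 carriers; normal, t5 and lognormal errors; nominal 5%). The pooled-variance test rejects 4.6–5.6% of the time with equal SDs, 1.7–2.4% if the active SD is 1.5 times placebo, and 0.8–1.2% at 2 times. Protocol section 5 expects more variability on active treatment, so this test would be conservative. Within-arm residual resampling stays at 4.6–5.6%.

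**Gene-level power** (simulated; White, active-only, ten variants of MAF 0.5%, 0.6 SD each, nominal 5%).
- All ten in the same direction: burden 80%, variance-component 45%, best single locus 25%.
- Half of them acting: 29%, 23%, 15%.
- Opposite directions: 8%, 46%, 26%.

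**Multiplicity.** Power of 80% at 5% means a standardised effect of 2.80. At 0.05/6 the critical value is 2.638, and Φ(2.80 − 2.638) = 56%. At 0.05/36 (six genes, three outcomes, two subgroups) it is 3.197, and Φ(2.80 − 3.197) = 35%.

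**The case against.** The strongest reply is that the interaction analysis no longer leads. The active-only analysis comes first and needs no placebo carriers. This stands, and it limits the main figures to the parallel analysis. It does not remove the problem: about four carriers per subgroup is still few, and the Analytic Plan does not say whether the White/Black restriction carries over.

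Second, the 1% cut-off is not the plan's. If rare means anything below the 5% used for the secondary analyses, the shortage is moderate at 2–3% and nearly gone at 5%. This also stands.

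Third, the subgroups need not be analysed separately. Table 1 has a column for all participants, and the restriction to White and Black does not exclude a combined model. Pooling roughly halves the 81%/88% figures, though about 2 SD would still be the smallest detectable interaction.

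Fourth, Table 1 already shows power of 0.001 in each subgroup at MAF 0.1, so the plan does not hide how weak subgroup interactions are. This is fair. Because a two-sided test cannot have power below its own significance level, that entry also implies a threshold near 0.001 or stricter. The nominal-5% detectable effects above are therefore optimistic.

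A reader might infer three stronger points. One is that the sponsor never considered power for rare variants; Figure 2 is not shown, so the documents cannot support that. Another is that sparse interaction tests produce excess false positives; the simulations show nominal or conservative size. The last is that the whole genetic aim fails; the lead analysis and the common variants are outside this point.

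**Conclusion.** The point holds for the single-locus interaction analysis of rare variants, now run in parallel. At MAF 1%, four in five White tests and nearly nine in ten Black tests would rest on two or fewer placebo carriers, and between a fifth and a third would be inestimable. Pooling brings this to 49% (White and Black combined) or 34% (all), with detectable effects near 2 SD. The active-only analysis is better but still thin within subgroups.

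The result rests on an assumed MAF, Exam 5 racial shares applied to 682 enrollees, and Hardy-Weinberg sampling. The percentages are expected shares of tests, not counts. Dropout and missing genetic consent would make them worse. The plan should be changed, but this does not threaten the trial. Confidence is medium, because the variant frequencies in the six genes are not in the documents.

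**What to change.** 1. Define rare by carrier count, separately for each analysis. For example, require 5 active carriers for active-only (detectable 2.80/√5 = 1.25 SD) and 5 placebo carriers for the interaction (with 15 active carriers, 2.80 × √(1/5 + 1/15) = 1.45 SD). Any variant that misses the minimum joins that analysis's gene-level set. A fixed 1% cut-off combined with a carrier minimum would leave a gap: 82%/91% of variants at MAF 2%, and 54%/71% at 3%, would miss the placebo minimum without being aggregated. Count carriers before outcomes are analysed.
2. For those variants, pre-specify a gene-level test in each of the six genes, in both analyses. Use a burden test together with a variance-component test, or one combined test, so that opposite-direction effects are covered. Allow for unequal arm variances in the interaction test.
3. Report single-locus results below the minimum as descriptive, and do not read their nulls as absence of modification.
4. State whether the active-only analysis keeps the White/Black restriction, and whether the two groups are analysed separately or combined.
5. Quote gene-level power after correction: a nominal 80% is about 56% across six genes, and about 35% across six genes, three outcomes and two subgroups.

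The cost is SAP wording and modest programming on genotypes already held. The downsides are real. Conclusions are per gene, not per variant. A burden test alone loses to single-locus testing when effects oppose (8% against 26%). Gene-level interaction also stays weak when few participants carry any rare variant: if 5% carry one, the detectable shared effect is still 1.7/1.85 SD White/Black at nominal 5%.

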	Exclusion criteria 
1. Current use of >1,000 international units (IU) of cholecalciferol daily2. Current use of any activated vitamin D product (calcitriol, paricalcitol, hectorol)3. Known history of allergy or adverse reaction to vitamin D treatment4. Known clinical history of primary hyperparathyroidism5. Known clinical history of kidney stones within the previous 5 years6. Known clinical history of kidney dialysis or transplant.7. Known clinical history of sarcoidosis8. Self-reported history of having elevated serum calcium levels9. Serum calcium level >11 mg/dl at MESA Exam 1 (2000-2002)10. Current participation in another interventional study11. Inability to provide written informed consent
Study Duration	16 weeks
Treatment, Dosage, and Route of Administration	2,000 IU cholecalciferol or inactive placebo taken by mouth once daily
Efficacy Assessments	Change in serum 1,25-dihydroxyvitamin D concentration, serum parathyroid hormone concentration, and blood pressure from baseline to 16-week follow-up visit.

Safety Assessment	Change in urine and serum concentrations of calcium and phosphate from baseline to 16-week follow-up visit. Research staff will assess adverse effects during the study duration by participant self-report.
Modifying Characteristics	The following characteristics will be evaluated for their influence on the biological response to cholecalciferol treatment: genetic polymorphisms, serum concentrations of vitamin D metabolic markers, race, gender, and body mass index.
Statistical Methods	Linear models will be constructed for the follow-up value of each outcome variable. Models will include the initial value of the outcome variable, treatment assignment, and the interaction of treatment with the potential modifying variables.
Date of protocol	February 5, 2018

ABBREVIATIONS

MESA = Multi Ethnic Study of Atherosclerosis

1,25(OH)₂D = 1,25-dihydroxyvitamin D, the activated form of the hormone

25(OH)D = 25-hydroxyvitamin D, the accepted marker of vitamin D storage

Vitamin D₃ = cholecalciferol, the active treatment in the study

PTH = parathyroid hormone

IU = international units

UV = ultraviolet

AE = Adverse event

SAE = Serious adverse event

GFR = glomerular filtration rate

CHSCC = Collaborative Health Studies Coordinating Center

NORC = Nutrition and Obesity Research Center

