5. RANDOMIZATION

Randomization will be performed centrally by the MESA data coordinating center (University of Washington, Seattle) in blocks of variable size (4-12), stratified by MESA study site.

Participants will be assigned to active vitamin D₃ or placebo in a 3:1 ratio, because short-term variability in response is expected to be substantially larger among participants who are assigned to active treatment.

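### The listed model terms leave out site, the only randomisation stratum, and the plan does not say how the treatment-only and genome-wide genetic models handle race or ancestry

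*Combined protocol and SAP*

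**What the plan says.** Section 5 (Randomization) assigns participants 3:1, centrally, "in blocks of variable size (4-12), stratified by MESA study site". No other stratum is named.

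Section 10 (Analytic Plan of the protocol) regresses the follow-up value of each outcome on treatment, allele count, their interaction, the baseline value, and "the following preselected precision variables: age, gender, BMI, season, and the estimated glomerular filtration rate (GFR". The Protocol Summary is shorter: "Models will include the initial value of the outcome variable, treatment assignment, and the interaction of treatment with the potential modifying variables".

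In section 10, race/ethnicity enters as a candidate modifier and as a restriction: "we will conduct primary genetic analyses among only the white and Black subgroups", with leads then taken to the other two groups. The secondary genome-wide analysis uses variants "derived from the Affymetrix 6.0 chip and 1000 Genomes imputation using the regression framework described above". The restriction is not repeated there. Table 1 gives power for All, White and Black.

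The later Analytic Plan, under Changes to the analytic plan, puts a new analysis first: "we will start by evaluating only participants who are treated with active vitamin D to assess main effects of genetic polymorphisms and clinical characteristics". It adds: "In parallel we will present analytic results from our original approach, in which we analyze all participants". It lists no covariates and no racial grouping for the treatment-only step.

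**The concern.** There are two separate gaps.

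**Site.** When assignment is balanced within site, a model that ignores site leaves between-site variation in the residual. The reported standard error then overstates the true variability of the treatment estimate. Genotype is not balanced within site, so the genotype-by-treatment estimate, which is closer to the trial's aim, loses some real precision.

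**Race and ancestry.** Genotype is not randomised. The protocol's Introduction says that one outcome, 1,25(OH)₂D, runs higher in African Americans, and it suspects differences in utilisation or catabolism. If races are pooled without a race term, a variant that does nothing but differs in frequency by race can take the credit for such a difference. The treatment-only analysis is the most exposed, because it has no placebo contrast to cancel differences unrelated to treatment.

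**Working it through.** The plan states no figure on this point, so there is none to reproduce. The check has three steps: a comparison of the model statements, then two calculations on assumed inputs.

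**1. What each place lists**

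| Place | Site | Race/ancestry covariate | Race restriction |
|---|---|---|---|
| Protocol Summary | no | no | none stated |
| Section 10, primary genetic | no | no | White and Black |
| Section 10, genome-wide | no | no | not stated |
| Changes to the analytic plan, treatment-only | not stated | not stated | not stated |

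**2. Omitting site**

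Inputs from the documents: N = 682 and 3:1 allocation. Assumed: outcome SD 1, baseline/follow-up correlation 0.7 (residual variance 1 − 0.7² = 0.51), and between-site SD τ given baseline.

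- Reported SE of the treatment effect without site: √[(0.51 + τ²)/(682 × 0.75 × 0.25)]. For τ = 0.3 this is √(0.60/127.9) = 0.0685. With site in the model it is √(0.51/127.9) = 0.0632.
- In simulation at τ = 0.3, the true SD of the estimate was 0.0636 with or without site. Only the reported SE is wrong. Type I error was 3.7%; the approximation 2Φ(−1.96 × 0.0685/0.0632) gives 3.4%.
- The SD of the genotype-by-treatment estimate was 0.107 without site and 0.100 with it, a rise of about 7%.
- For τ = 0.1 the reported SE is too large by a factor of √(0.52/0.51) = 1.01, and type I error is 4.8%.
- If sites differ by a stable 0.3 SD in level, baseline adjustment leaves 0.3 × 0.3 = 0.09, and type I error is again 4.8%.

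**3. Pooling White and Black without a race term, treatment-only model**

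Inputs from the documents: section 12.1 gives 44% Caucasian and 36% African American in the source population. That makes 682 × 0.75 × 0.44 = 225 and 682 × 0.75 × 0.36 = 184 treated, 409 in all, with White share 0.55. Assumed: correlation 0.7 as above, a stable race gap L in outcome level, and allele frequencies by race.

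- Gap left after baseline adjustment: δ = 0.3L, which is 0.045 for L = 0.15 and 0.090 for L = 0.30.
- Genotype variance at frequencies 0.2 and 0.4: within race 0.55 × 0.32 + 0.45 × 0.48 = 0.392; between races 0.55 × 0.45 × 0.4² = 0.0396; total 0.432.
- Spurious slope: b = 0.55 × 0.45 × 0.4 × δ/0.432, which is 0.0103 and 0.0206.
- Non-centrality: λ = b√(0.432 × 409)/0.714, which is 0.19 and 0.38.
- Type I error: Φ(λ − z) + Φ(−λ − z). At a 5% test this gives 5.4% and 6.7%; simulation gave 5.7% and 6.7%.

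The same formula gives 5.1% and 5.5% at frequencies 0.2 and 0.3, and 6.5% and 11.2% at the wide contrast of 0.1 and 0.5. With a race term, simulation returned 4.7% to 5.2%. With change scores, which cancel a stable gap, it returned 4.9% to 5.2%.

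**Threshold.** The readable text gives no alpha. Table 1 shows power of 0.001 at allele frequency 0.1 in both subgroups. An unbiased two-sided test cannot have power below its alpha, so the planning alpha was about 0.001 or less. At 0.001 (z = 3.29), frequencies 0.2 and 0.4 give 0.12% and 0.19%.

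**Interaction model.** With White and Black pooled (n = 545 = 682 × 0.80) and race not modifying response, the simulated test held at 4.7% to 5.1%. With an assumed race difference in response of 0.15 to 0.30 SD and frequencies 0.2 and 0.4, it ran at 5.8% and 8.5%. A race main effect left it at 5.8% and 8.7%; adding race by treatment gave 4.8% and 4.5%.

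**The case against.** The Analytic Plan section is a memo of changes, and it says that the overall design stands. Items it does not mention plausibly carry over from section 10: the baseline value, the five covariates and the White/Black restriction. The genome-wide sentence also points back to the earlier framework. Figure 2, which accompanies the treatment-only analysis, is not shown in the text available and counts neither way. All this stands. A reader might infer that the plan pools races without adjustment, but the documents do not say so. They leave the matter unstated, because the restriction is worded for the primary genetic analyses only.

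The memo describes effects of "genetic polymorphisms and clinical characteristics on the changes in study outcomes", and change scores would cancel a stable level gap. But the protocol calls its outcomes changes throughout while modelling follow-up given baseline, so the wording cannot be relied on to signal change scores.

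On site, stratification concerns the treatment contrast, and the treatment-only analysis has none. Assays are run in one central laboratory and field procedures are identical, so a site SD of 0.3 given baseline looks high for the biochemical outcomes. That is fair, and it is why the site point is minor. It does not explain leaving the stratum out of an explicit term list when including it costs almost nothing.

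**Conclusion.** Both gaps are real and modest.

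**Site.** The stratum is missing from every stated model. A reader might infer a biased treatment effect. That does not follow: the estimate is unbiased, its variability is unchanged, and its test errs on the conservative side. The real loss is in the interaction estimate, about 7% in SD at an assumed site SD of 0.3 and negligible at 0.1. The documents give no site effects.

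**Race and ancestry.** Handling is unstated for the genome-wide and treatment-only genetic models. If they are pooled and unadjusted, inflation is small to modest under stable level gaps of 0.15 to 0.30 SD: 5% to 7% at a 5% test, or 0.12% to 0.19% at 0.001, for frequencies 0.2 and 0.4. It grows if race differs in change itself. A reader could reach far higher error rates by assuming large race gaps together with extreme frequency contrasts, but no document supports those inputs. The documents give no allele frequencies, race gap or alpha, so all these figures are scenarios. The parallel interaction analysis is a partial safeguard that weakens if race modifies response, which section 10 itself sets out to test.

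**What to change.** 1. Add four site indicators, for five field centers, to every model. This costs four degrees of freedom out of 682.
2. For the treatment-only analysis, state the covariates, whether the White/Black restriction carries over, and whether the response is change or follow-up given baseline.
3. Run the treatment-only and genome-wide genetic models within race/ethnicity groups. Where groups are pooled, add race/ethnicity and a few ancestry components from the existing array, and add race by treatment in pooled interaction models.

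The change is to plan wording only. Race/ethnicity takes one to three degrees of freedom, and the components and treatment interactions take a few more. Adjusting a pooled model for race gives up the between-race part of genotype variation: 0.0099/0.375 = 3%, 0.0396/0.432 = 9% and 0.158/0.482 = 33% at frequencies 0.2/0.3, 0.2/0.4 and 0.1/0.5. Components exist only for participants with array data. Terms should be few within race groups, since only about 682 × 0.25 × 0.36 = 61 Black participants would be on placebo.

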3. STUDY DESIGN

This study is double blind, parallel design, randomized clinical trial that will compare treatment with 2,000 international units of cholecalciferol daily by mouth *versus* inactive placebo. Eligible participants will be randomly assigned to receive cholecalciferol treatment or placebo in a 3:1 ratio for a total duration of 16-weeks. The planned sample size is 1,600. Study outcomes are changes in serum concentrations 1,25-dihydroxyvitamin D and parathyroid hormone after 16-weeks. Study procedures will take place at five existing MESA field centers.

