Brief statement of the problem

The Individualized Response to Vitamin D Treatment (INVITE) trial was designed to identify clinical, genetic, and biomarker differences across individuals in response to cholecalciferol therapy. The trial was originally conceived to address two emerging research directions within the National Heart Lung and Blood Institute (NHLBI):

1. Innovative use of existing observational cohort studies to include nested clinical trials
2. A personalized medicine approach that includes testing individualized responses to treatments, including clinical and genetic characteristics.

The INVITE trial is nested within the NHLBI sponsored Multi-Ethnic Study of Atherosclerosis (MESA). Participants are recruited from four MESA clinical sites at the time of their 6th examination. Recruitment for the INVITE trial has been lower than anticipated due to:

[figure not shown]
1. Overall turnout for MESA Exam 6 was considerably lower than expected, particularly at the Wake Forest site, which is a primary INVITE recruitment site.
2. The INVITE grant was funded after MESA Exam 6 was already underway.
3. The use of high-dose cholecalciferol supplementation was greater than expected.

We have implemented several procedures to increase recruitment, including the creation of specialized visits for participants who already completed MESA Exam 6, the inclusion of an optional washout period for pre-existing vitamin D users, and the addition of a 5th MESA recruitment site. Each of these procedures have increased enrollment; however, the final anticipated sample size will be 682.

Changes to enrollment

As of September 1, 2018, the MESA INVITE study had enrolled 523 participants. We now plan to enroll 682 participants by January 18, 2019, at which time we will close enrollment. We are currently on track to meet this goal based on the current rate of recruitment (below). With 16 weeks of scheduled follow-up for each participant, we plan to complete all study visits by May 30, 2019.

Figure 1. Enrollment in MESA INVITE

Changes to the analytic plan

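### Table 1 appears to give interaction power for the 1,600-participant design, and the readable plan does not restate it for 682, where the detectable treatment-by-allele interaction is 1.53 times larger

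*Combined protocol and SAP*

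**What the plan says.** Protocol section 3 sets the size: "The planned sample size is 1,600", allocated 3:1. Section 10 specifies a linear model for each follow-up outcome that contains treatment, minor-allele count and their interaction. It then states "Power to detect genetic associations of common variants are shown in Table 1". Table 1 gives power by minor allele frequency (MAF) for All, White and Black participants. The best cell is 0.521 (All, MAF 0.4) and the lowest cells are 0.001 (White and Black, MAF 0.1). The table prints no sample size, alpha, sidedness, per-allele effect or tested term. On the analysis set, section 10 says "Primary analyses will include participants who complete baseline and 16-week follow-up regardless of adherence".

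The Analytic Plan, under its statement of the problem, says "the final anticipated sample size will be 682". It starts from a new analysis of actively treated participants only, but retains the interaction test: "In parallel we will present analytic results from our original approach, in which we analyze all participants and test the interaction". Under Changes to sample size and study power it says "Study power for the treatment only analytic approach is considerably greater than that of the original interaction-based analyses", and then "Under the anticipated sample size of 682, the INVITE study will maintain power to detect clinically relevant associations". The one display it describes at the new size is Figure 2, captioned "Minimal detectable associations for genetic polymorphisms under a treatment-only analysis".

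**The concern.** The interaction test is still to be reported, but its only readable power statement belongs to a design with more than twice as many participants. A reader who takes Table 1 at face value will credit the test with power that the trial no longer has.

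This matters because the two analyses answer different questions. A treatment-only association between genotype and change in PTH, 1,25(OH)₂D or urine calcium may be modification of the vitamin D effect. It may also be a genotype-related change that would occur on placebo, and only the comparison with placebo separates the two. If a positive treatment-only result appears beside a null interaction, readers need to know what size of interaction the trial could have detected. Without that, the null may be misread as evidence against modification.

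The point covers the common-variant interactions in Table 1. It does not extend to rare variants or to the clinical and biomarker modifiers, which Table 1 does not address.

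**Working it through.** **Inputs.** Planned N 1,600 (Protocol section 3); revised N 682 and unchanged 3:1 allocation (Analytic Plan); twelve power cells (Table 1). Alpha, sidedness, effect size and outcome SD are not stated.

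**Can Table 1 be reproduced?** Not from the documents, because those four inputs are missing. The check therefore rescales the printed cells and holds everything but N fixed.

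**Step 1: the factor that needs no alpha.** Information is proportional to N: 682/1,600 = 0.426. The noncentrality d of the interaction test scales with sqrt(0.426) = 0.653. At any given alpha and power, the detectable per-allele interaction grows by 1/0.653 = 1.53.

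**Step 2: what the table implies about alpha.** Two-sided power cannot be below alpha. A cell printed as 0.001 is below 0.0015, so if all columns share one alpha, it is below 0.0015. If White and Black could have a different alpha from All, only the All column's lowest cell (0.013, so below 0.0135) bounds the alpha for All.

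**Step 3: rescale the best cell.** Solve d from Φ(d − z) + Φ(−d − z) = 0.521, where z is the critical value. Then evaluate the same expression at 0.653d. For a one-sided test, drop the second term. For example, at two-sided alpha 0.0015, z = 3.175, d = 3.227 and 0.653d = 2.107, so power is 0.143.

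| Alpha | Two-sided power at 682 | One-sided power at 682 |
|---|---|---|
| 0.0135 (All column only) | 20.5% | 23.2% |
| 0.0015 (one alpha for all columns) | 14.3% | 16.0% |
| 0.001 | 13.4% | 15.0% |
| 1e-5 (illustrative) | 6.7% | 7.4% |
| 5e-8 (illustrative) | 3.2% | 3.5% |

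**Step 4: other cells at two-sided alpha 0.0015.** The All column at MAF 0.1, 0.2, 0.3 and 0.4 goes from 1.3, 14.1, 35.7 and 52.1% to at most 0.5, 3.6, 9.0 and 14.3%. At MAF 0.4, White goes from 8.3% to at most 2.2%, and Black from 4.1% to at most 1.3%.

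**Step 5: where in the range the table points.** One alpha and one scale constant were fitted to all twelve cells, taking All as White plus Black in the ratio 55:45 (from 44% and 36% in section 12.1). At alpha 5e-8 the largest miss is 0.019; at 0.001 it is 0.129. The pattern therefore suggests a very small alpha and a best cell near 3% at 682. This is indirect evidence, not a stated input.

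**Step 6: sensitivity to the fixed quantities** (two-sided alpha 0.0015; both ranges assumed).
- Race mix: suppose All means White plus Black and their share moves from 80% (44% + 36%) to 70% or 90%. The factor becomes 1.64 or 1.44, and the best cell 11% or 17%.
- Completion: suppose 90% or 80% of the 682 are genotyped completers (614 or 546) and Table 1 used the full 1,600. The factor becomes 1.61 or 1.71, and the best cell 12% or 10%. If Table 1 was already net of the same proportional losses, the factor stays at 1.53.

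**The case against.** The strongest reply is that the plan is already candid. It has a section on the change in size and power, says the treatment-only approach has considerably more power, and records review and approval by the DSMB. The sentence on maintained power follows that comparison and leads to a treatment-only figure. In context it is defensible as a treatment-only claim. A reader might infer that the sponsor claims to have kept interaction power at 682, but the passage does not support that. What stands is narrower: the sentence is worded for the whole study, and the admission compares two methods without saying how far interaction power fell with N.

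Second, the basis of Table 1 is inferred. Its position after the interaction model, and the Analytic Plan's description of the earlier approach as interaction-based, make the reading natural but do not prove it. A reader might also infer that the table was miscalculated. Nothing shows that: no cell is contradicted, and the objection is only that the table belongs to a superseded N.

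Third, the fall to about 14% is not an unconditional ceiling. It needs a two-sided test, one alpha across columns, and an unchanged race mix and completion rate. The Analytic Plan reports a shortfall concentrated at one site and the addition of a fifth, so the race mix may have moved. This objection stands, and the result is given as a range for that reason.

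Fourth, Figure 2 cannot be seen and may show more than its caption says. That also stands and limits confidence.

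Finally, Table 1 was already pessimistic: ten of its twelve cells are below 15%. This lowers the weight of the point. It does not remove the need to state the current figure, since 52% and a value somewhere from 3% to 23% support different readings of a null result.

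**Conclusion.** The point holds as a stale power statement. On the natural reading of Table 1, the current design does not deliver the interaction power printed there, and the readable text does not say what it does deliver. The firm figure is the 1.53-fold larger detectable interaction. It assumes that Table 1 was computed for the 1,600 design and that the 3:1 split, variances, race mix and completion rate are unchanged. The power figures in the table under Step 3 rest in addition on the unstated alpha and sidedness, so none of them should be quoted as a single answer.

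The weight is minor to moderate: worth correcting, but with no effect on the validity of either analysis. Confidence is moderate, because the basis of Table 1 is inferred and Figure 2 is not visible.

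**What to change.** - Recompute Table 1 at 682 and at the expected number of genotyped completers, using the race mix actually enrolled.
- Print the tested term, alpha, sidedness, per-allele effect and N for each column.
- Put the restated interaction power, or the minimal detectable interaction, beside Figure 2. If Figure 2 already shows it, say so in the text.
- Limit the sentence on maintained power to the treatment-only analysis.

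The cost is one recalculated table and one reworded sentence. The stated interaction power will look less favourable. Enrolment, design and analysis do not change.
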